### 5.4. Safety Analyses

All safety analyses will be performed on the FAS or FAS7.

The presentation of the safety data is divided into 2 parts, one set of tables will be created for the entire active follow-up period covering the double blind and open-label active phase until site approval of PA7 and another set of tables will be created for the passive follow-up period covering

the safety data from site approval of PA7 until study end. The first set of tables covering the active follow-up is performed on the FAS and the second set of tables covering the passive follow-up is performed on FAS7.

No formal statistical testing of safety data is planned. All safety analyses will be presented overall and no presentations by subgroups are planned.

#### **5.4.1. Safety data collected**

The following information will be collected for:

- All participants in the FAS during the entire study (including the passive follow-up phase):
  - Serious adverse events (SAEs) and medically-attended adverse events (MAAEs) leading to study discontinuation after each vaccination
  - AEs of Special Interest (AESI)
  - Selected AEs of interest (AEI), see Appendix 6 for details
- All participants in the FAS until 6 months after last vaccination:
  - MAAEs after each study vaccination

#### **5.4.2. Study Phases**

A baseline (or reference) value will be defined as the value of the last available assessment prior to the first study vaccination on Day 1.

The safety analyses will present all results by study phase (see Section [5.4.3](#)).

Study day or relative day is defined as follows:

- Study Day = visit date – date of Day 1 + 1; if visit date  $\geq$  date of Day 1 (date of first vaccination).
- Study Day = visit date – date of Day 1; if visit date  $<$  date of Day 1 (date of first vaccination).

#### **5.4.3. Phase Definitions**

COVID-19 vaccinations given outside of the study reported under the concomitant medications will be included in the phase definitions as active vaccinations together with the study vaccinations. Subjects that have COVID-19 vaccinations on the same day or before the date of informed consent will not have a screening phase. Their first phase/period will be post-dose 1 starting from the first COVID-19 vaccination given outside of the study. Note, placebo vaccination between active vaccinations will be ignored.

For the safety data after PA7 approval, no separate phase will be created. Events that occurred in the passive follow-up phase will be flagged, and follow-up in the passive phase is calculated separately starting from the PA7 study site approval date until end of the phase or end of study.

The phases in the study will be constructed as follows:

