### **1.1. Objectives, Endpoints**

The list of objectives and endpoints for the open-label active surveillance phase and for the open-label passive follow-up phase can be found in PA7. Note that no efficacy evaluations or group comparisons will be performed. All objectives will be evaluated using descriptive statistics.

As of protocol amendment 2, subjects were allowed to receive vaccination outside of the study while still following the same protocol scheduled procedures as those subjects that remained in the study with the Ad26.COV2.S vaccine. The safety for subjects that received other vaccines outside of the study will also be described. No tabulations of efficacy data following vaccines received outside of the study will be provided.

The exploratory endpoints associated with the correlate of risk/efficacy objective will not be evaluated in this study. Correlate of risk/efficacy objectives will be evaluated in the context of study COV3001.

The exploratory endpoints associated with immunogenicity objectives will not be evaluated in the open-label active surveillance phase.

Estimands for the open-label active surveillance analysis:

Objectives	Endpoints/Variable	Population	Intervention	Intercurrent events	Summary measure
Safety	SAEs, AEIs and AESIs from study start until PA7 site approval	Adults>= 18 years old	Ad26.COV2.S, placebo, one or more doses of mRNA + Ad26.COV2.S OR one or more doses of non-mRNA + Ad26.COV2.S, mixed schedule	LTFU	Number of subjects with events and incidence rates per 100 person years per reporting period
Molecularly confirmed a , symptomatic COVID-19 b	Symptomatic COVID-19 according to mild, moderate or severe programmed algorithmic definition, with onset at least 28 days after last vaccination.	Adults>= 18 years old	Single dose Ad26.COV2.S  Two doses Ad26.COV2.S (maximum of 70 days between doses)  Booster dose Ad26.COV2.S (minimum of 71 days between doses)	LTFU-Outside vaccinations	Number of subjects with events and incidence rates per 100 person-years

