#### **5.1.1.2. Analysis Scope**

The analysis of safety will include safety data collected from the beginning of the study until study site approval of PA7 for each participant. The vaccination groups that will be presented are: placebo, Ad26.COV2.S, non-mRNA (any number of doses) + Ad26.COV2.S booster or mRNA (any number of doses) + Ad26.COV2.S booster, and mixed schedule group. The safety data will be presented in three separate layouts: layout 1a covers the safety data after Ad26.COV2.S and placebo only, up until receipt of another COVID-19 vaccine; layout 1b covers the safety data after Ad26.COV2.S when given as a booster on top of mRNA vaccinations or on top of non-mRNA vaccinations, layout 2 covers all other safety data after outside vaccinations or any other order

mixing outside vaccination with Ad26.COV2.S vaccination (eg: Ad26.COV2.S + mRNA vaccination).

The efficacy analysis planned for the open-label active phase, comparing the different study cohorts, will include efficacy data from the date of unblinding up to 30 days prior to study site approval of PA7. This 30 day window is chosen to assure that the active surveillance took place for the full duration of the COVID-19 episode and no symptoms would be missed. A separate listing will be provided to include the COVID-19 events within 30 days prior to study site approval of PA7. There are 3 study cohorts: one dose schedule; two-dose schedule and booster dose schedule. These cohorts are described in more detail in Section [5.2.1](#).

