placebo after an active vaccination, the placebo injection will not be counted as a study vaccination.

When the time of the first study vaccination is missing and it occurred on the same day as the randomization, the time of vaccination will be imputed with the time of randomization. Otherwise, if the date of first vaccination is available, then the time will be imputed with 00:00 before applying the phase and period derivation rules.

In case the time of the vaccination outside the study is missing then time will be imputed with 00:00 if the date is available. In case of a partial date, then the available info will first be compared to the unblinding date and, if no imputation can be done, then the available info will be compared to the date of informed consent. If the month and year are available and they are the same as the unblinding month and year then the day is imputed with the day of unblinding, else if the month and year are the same as the informed consent month and year then the day is imputed with the day of informed consent, otherwise the day is imputed with the first day of that month. If the month and day are missing then the year will be compared with the year of unblinding. If the year is the same then the month and day are imputed with the day and month of the unblinding date, else if the year is the same as the informed consent year then the month and day are imputed with the day and month of informed consent, otherwise the other vaccine date is imputed with the first of January of that year. If the date and time of the outside vaccination is fully missing, then the date is imputed with the ICF date.

For subjects that initially receive placebo and subsequently receive active vaccinations, separate post-dose periods will be created for the placebo injections and the active vaccinations. For subjects that receive placebo after an active vaccination, no post-dose period or follow-up periods for the placebo injection will be created.

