**C. Layout 2:**

**1. Mixed schedule**

The safety data after all other vaccination schedules will be included here. This includes safety data after receipt of only outside vaccinations, after outside vaccinations when primed with Ad26.COV2.S, after outside vaccinations prior to first Ad26.COV2.S vaccination, or any other combination switching between outside vaccinations and Ad26.COV2.S. Note that participants who have a vaccination given outside of the study on the same day as the first study vaccination will have all safety data presented in the mixed schedule vaccination group.

Subjects that switch between Ad26.COV2.S vaccinations and COVID-19 vaccinations given outside of the study (and vice versa) will be presented in the relevant vaccination group depending on the actual vaccination sequence. For example:

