**2. Vaccination sequence: outside COVID-19 vaccination, Ad26.COV2.S, outside COVID-19 vaccination**

Safety data for subjects following this sequence will have data following the first outside COVID-19 vaccination up to the date of the Ad26.COV2.S vaccination presented in the outputs for the mixed schedule vaccination group (layout 2). The data following the Ad26.COV2.S vaccination up to the date of the second outside COVID-19 vaccination will be presented in the outputs for Ad26.COV2.S after a COVID-19 vaccination given outside of the study (layout 1b) so long as the previous outside vaccinations were always mRNA or always non-mRNA. The data following the second outside COVID-19 vaccination will be presented in the outputs for the mixed schedule vaccination group (layout 2).

For outputs using layout 1a or 1b, all tables will be produced by study phases and periods per vaccination group, ie post-dose, follow-up D30-M6, follow-up M6-end. For the mixed schedule vaccination group (layout 2) only the AE summary table will be produced presenting data for the entire study period, ie not presented by study phases.

The safety analyses will be performed for the combined double-blind and open-label active phase for the FAS.

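### SAP 5.4.3 starts safety time at an outside vaccine given before consent, against the plan's own study-period scope, so mixed-schedule rates in one table may be slightly low

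*SAP*

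**What the plan says.** SAP 5.4.3 treats outside COVID-19 vaccines as active vaccinations when it builds the safety phases. It then adds a special rule: "Subjects that have COVID-19 vaccinations on the same day or before the date of informed consent will not have a screening phase". The next sentence fixes the start: "Their first phase/period will be post-dose 1 starting from the first COVID-19 vaccination given outside of the study". Table 6 likewise opens post-dose 1 at the first vaccination and gives no lower limit at consent. The text after Table 6 says that, for reporting, the post-dose and follow-up phases after an outside vaccine are merged into one overall period.

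Section 5.4.4 assigns this time to layout 2. The mixed-schedule group includes data "after outside vaccinations prior to first Ad26.COV2.S vaccination", and the second worked example there has "data following the first outside COVID-19 vaccination up to the date of the Ad26.COV2.S vaccination presented in the outputs for the mixed schedule vaccination group". That group gets one AE summary table, over the whole study period rather than by phase.

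Section 5.4.6.2 makes the rate denominator the vaccination group's person-years in the phase. The safety estimand in 1.1 lists mixed schedule among the interventions to be summarised per 100 person-years.

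On scope, 1.1 names the endpoint as "SAEs, AEIs and AESIs from study start until PA7 site approval" and 5.1.1.2 states: "The analysis of safety will include safety data collected from the beginning of the study until study site approval of PA7 for each participant". Sections 5.4 and 5.4.4 describe the same set of tables as covering the double-blind and open-label active phases.

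**The concern.** A rate needs events and person-time from the same window. The scope statements start the data at the beginning of the study. The phase rule lets the clock start at a vaccine given before the participant had consented. If the clock is taken from the phase dates, some participants add person-time during which few or no adverse events could have been recorded, and the rate falls for a reason unrelated to safety. Two programmers following this SAP could report different mixed-schedule denominators.

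The stake is small: the incidence rates of one group in one descriptive table.

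**Working it through.** The SAP gives no figure on this point, so there is none to reproduce. The check traces the text and then illustrates the size.

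**Does pre-consent time reach a denominator?**

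1. Start: 5.4.3 and Table 6 open post-dose 1 at the outside vaccine, even before consent.
2. Group: 5.4.4 places the time from that vaccine to the first Ad26.COV2.S dose in mixed schedule.
3. Period: the text after Table 6 merges the phases following an outside vaccine, so the merged period inherits the start in step 1.
4. Denominator: 5.4.6.2 counts person-years over that time.
5. Other start rules: 5.4.8 defines follow-up for the other groups and leaves the mixed-schedule group out.

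Nothing in this chain cuts the time at consent.

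**What is outside the problem?** Layouts 1a and 1b start at a study vaccination (5.4.4). Passive-phase follow-up starts at site approval of Protocol Amendment 7 (5.4.3). Percentages use participant counts (5.4.6.2). The whole-study summary in 5.4.6.1 shows only numbers and percentages.

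**How large could it be?** Four inputs are needed, and all are assumptions:

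- q: share of the mixed group vaccinated outside before consent
- g: their mean gap from that vaccine to consent, in months
- T: mean mixed-schedule follow-up after consent over the whole group, in months
- c: completeness of pre-consent AE recording relative to later (0 = none)

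At a constant event rate, the reported rate divided by the rate on observed time is (T + c·q·g)/(T + q·g). The understatement is therefore (1 − c)·q·g/(T + q·g). With c = 0:

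| g, T (months) | q = 1% | q = 5% | q = 10% |
|---|---|---|---|
| 1, 24 | 0.04% | 0.21% | 0.41% |
| 1, 12 | 0.08% | 0.41% | 0.83% |
| 3, 12 | 0.25% | 1.23% | 2.44% |
| 6, 24 | 0.25% | 1.23% | 2.44% |
| 6, 12 | 0.50% | 2.44% | 4.76% |
| 6, 6 | 0.99% | 4.76% | 9.09% |

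For example, g = 6, T = 12, q = 1% gives 0.06/12.06 = 0.50%. Setting c = 0.5 halves every entry.

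The share needed for a 1% understatement at c = 0 is q = (0.01/0.99)·T/g: 1.0% at (6, 6), 2.0% at (6, 12), 4.0% at (3, 12) and 12.1% at (1, 12).

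**Do the date rules change the gap?** They work both ways.

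- Shorter: "If the date and time of the outside vaccination is fully missing, then the date is imputed with the ICF date", which makes the gap zero. A missing day in the consent month also goes to the consent date, unless that is also the unblinding month.
- Longer: if the month matches neither unblinding nor consent, "otherwise the day is imputed with the first day of that month", which is 0 to 30 days too early. If only the year is known and it matches neither year, the date becomes 1 January, up to 364 days too early (365 in a leap year).

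Moving every affected date back by about a month takes the (q = 1%, g = 6, T = 12) case from 0.50% to 0.07/12.07 = 0.58%. Neither rule can create a gap for a vaccine given after consent, because the first day of a later month or year is still after consent.

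**The case against.** The best defence is that the plan repeatedly says what period the safety tables cover. Sections 1.1, 5.1.1.2, 5.4 and 5.4.4 all point to the study itself, and 5.4.6.1 spells out the whole study period, for another table, as the sum of the study phases. Time before consent belongs to none of these. Section 5.4.3 also says its phases serve to prepare the analysis datasets and are regrouped for reporting, and a post-dose 1 anchored at the outside vaccine is needed to classify the sequence correctly. A careful programmer might therefore cut at consent unprompted.

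The scope statements do weigh against the literal calculation. But they limit which data are reported and give no start for person-time. The regrouping in 5.4.3 joins the phases after an outside vaccine without trimming them. The two sets of statements conflict, and the SAP does not say which governs.

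It is also fair that those affected are an edge case. The mixed group includes everyone vaccinated outside after a study dose, and they have no such gap. Consent is not the only possible start either: 5.4.8 uses the first study vaccination or first Ad26.COV2.S dose for other groups. For someone vaccinated outside before consent, consent and first study vaccination differ by at most the screening window, up to 28 days (1.2).

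A reader might infer a large bias, because one person's mixed-schedule time can lie mostly before consent. With an assumed 3-month gap (about 91 days) and 28 days of screening before an Ad26.COV2.S dose, the share is 91/(91 + 28) = 76%. The SAP reports no such subgroup; these participants are pooled with the rest. A reader might also infer that the rates for Ad26.COV2.S itself are diluted. The start rules of layouts 1a and 1b exclude that.

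**Conclusion.** The point holds as a minor inconsistency. Followed literally, the phase rule puts pre-consent time into the mixed-schedule denominator, against the plan's stated scope, and biases the rates per 100 person-years in the active-follow-up AE summary table slightly downward. With 1% of the group affected and no pre-consent capture, the understatement is about 0.04% to 1.0% over the gaps and follow-up times considered. The larger entries need shares of 5% to 10%, for which the SAP gives no basis. The true size cannot be found from the document and may be negligible.

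The direction rests on adverse events being recorded less completely before consent than after. That is inferred from the scope statements and from 5.4.1, which describes collection during the study; the SAP does not state when collection starts. No conclusion about the vaccine depends on this table's rates, and no safety testing is planned (5.4).

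**What to change.** In 5.4.3, keep the outside-vaccine date for classifying the vaccination sequence. Add that layout 2 person-time, and the window for adverse events counted with it, begin at the later of the outside-vaccination date and the informed consent date. State in 5.4.4 that the layout 2 reporting period begins there. Consent is a natural floor because Table 6 starts the phase structure at consent for everyone else.

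The cost is one or two sentences and a single maximum in the dataset derivation, with no new data. Mixed-schedule person-years can only stay the same or fall. Any adverse events recorded before consent leave this table and can be listed separately. The cut also removes the effect of imputed dates that fall too early before consent.

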**Table 6: Phase Definitions for Safety Analysis**

Phase	Phase #	Period	Period #	Interval	
				From	To
Screening	1			Date and time of signing the informed consent form	One minute prior to start of post dose 1 period
Post Dose	2	Post dose 1	1	Date and time of first vaccination	
Minimum of
 
 
a) 23:59 at the date of last contact (for early discontinuation or completion)
 
b) 23:59 at the date of database cut-off date
 
c) 23:59 on 28 days after the first vaccination (23:59 of day of vaccination + 28 days)
 
d) One minute prior to date and time of next vaccination
 

Follow-up 1 (D30-M6)	3			One minute after post-dose 1 period ends	
Minimum of:
 
 
a) 23:59 at the date of last contact (for early discontinuation or completion)
 
b) 23:59 at the date of database cut-off date
 
c) 23:59 at the date of Month 6 (date of vaccination + 6 months)
 
d) One minute prior to date and time of next vaccination
 

Follow-up 1 (M6-End)	4			One minute after follow-up 1 (D30-M6) ends	
Minimum of:
 
 
a) 23:59 at the date of database cut-off
 
b) One minute prior to date and time of next vaccination
 
c) maximum of: 
 
1. 23:59 at the date of last contact (for early discontinuation or completion)
 
2. 23:59 at the date of last visit (for completion )
 
 
 

Post Dose	2	Post dose 2	2	Date and time of second vaccination	
Minimum of
 
 
a) 23:59 at the date of last contact (for early discontinuation or completion)
 
b) 23:59 at the date of database cut-off date
 
c) 23:59 on 28 days after the second vaccination (23:59 of day of vaccination + 28 days)
 
d) One minute prior to date and time of next vaccination
 

Follow-up 2 (D30-M6)	5			One minute after post-dose 2 period ends	
Minimum of:
 
 
a) 23:59 at the date of last contact (for early discontinuation or completion)
 
b) 23:59 at the date of database cut-off date
 
c) 23:59 at the date of Month 6 (date of vaccination + 6 months)
 
d) One minute prior to date and time of next vaccination
 

**Table 6: Phase Definitions for Safety Analysis**

Phase	Phase #	Period	Period #	Interval	
				From	To
Follow-up 2 (M6-End)	6			One minute after follow-up 2 (D30-M6) ends	Minimum of: a) 23:59 at the date of database cut-off b) One minute prior to date and time of next vaccination c) maximum of: 1. 23:59 at the date of last contact (for early discontinuation or completion) 2. 23:59 at the date of last visit (for completion )
Post Dose a	2	Post dose 3	3	Date and time of third vaccination	Minimum of: a) 23:59 at the date of last contact (for early discontinuation or completion) b) 23:59 at the date of database cut-off date c) 23:59 on 28 days after the third vaccination (23:59 of day of vaccination + 28 days) d) One minute prior to date and time of next vaccination
Follow-up 3 (D30-M6) a	7			One minute after post-dose 3 period ends	Minimum of: a) 23:59 at the date of last contact (for early discontinuation or completion) b) 23:59 at the date of database cut-off date c) 23:59 at the date of Month 6 (date of vaccination + 6 months) d) One minute prior to date and time of next vaccination
Follow-up 3 (M6-End) a	8			One minute after follow-up 3 (D30-M6) ends	Minimum of: a) 23:59 at the date of database cut-off date b) One minute prior to date and time of next vaccination c) maximum of: 1. 23:59 at the date of last contact (for early discontinuation or completion) 2. 23:59 at the date of last visit (for completion )

(a) In case a treatment sequence has more than 3 vaccinations, the phases need to be added accordingly (Post-dose 4, Follow-up 4 (D30-M6), Follow-up 4 (M6-End), etc)

All vaccinations will have post-dose and follow-up phases as appropriate. The study phases are used to prepare the ADaM datasets, however for reporting purposes, some periods and phases will be combined and others will be renumbered. Specifically, after a COVID-19 vaccination outside the study, the post-dose and follow-up phases will be combined so that data after an outside vaccination can be presented as an overall period. The numbering of a post-dose period after an Ad26.COV2.S vaccination will be restarted at 1 in case that previous vaccinations were only outside vaccinations (only mRNA or only non-mRNA vaccinations) or were only placebo injections. Additionally, data following an Ad26.COV2.S vaccination will be censored at the date and time of a COVID-19 vaccination given outside of the study. Also for participants that receive

placebo after an active vaccination, the placebo injection will not be counted as a study vaccination.

When the time of the first study vaccination is missing and it occurred on the same day as the randomization, the time of vaccination will be imputed with the time of randomization. Otherwise, if the date of first vaccination is available, then the time will be imputed with 00:00 before applying the phase and period derivation rules.

In case the time of the vaccination outside the study is missing then time will be imputed with 00:00 if the date is available. In case of a partial date, then the available info will first be compared to the unblinding date and, if no imputation can be done, then the available info will be compared to the date of informed consent. If the month and year are available and they are the same as the unblinding month and year then the day is imputed with the day of unblinding, else if the month and year are the same as the informed consent month and year then the day is imputed with the day of informed consent, otherwise the day is imputed with the first day of that month. If the month and day are missing then the year will be compared with the year of unblinding. If the year is the same then the month and day are imputed with the day and month of the unblinding date, else if the year is the same as the informed consent year then the month and day are imputed with the day and month of informed consent, otherwise the other vaccine date is imputed with the first of January of that year. If the date and time of the outside vaccination is fully missing, then the date is imputed with the ICF date.

For subjects that initially receive placebo and subsequently receive active vaccinations, separate post-dose periods will be created for the placebo injections and the active vaccinations. For subjects that receive placebo after an active vaccination, no post-dose period or follow-up periods for the placebo injection will be created.

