#### **5.4.4. Vaccination groups**

All safety analyses will be tabulated by vaccination group according to the *as treated* principle. The COVID-19 vaccinations received outside of the study are considered as well. Participants can be present in more than 1 vaccination group as described below. Safety data by vaccination group will be analyzed descriptively.

The following vaccination groups will be presented:

A. Layout 1a:

1. Placebo

All participants who received as first vaccination a placebo injection. All safety data will be reported here until the participant receives an active COVID-19 vaccination (Ad26.COV2.S or outside vaccination).

2. Ad26.COV2.S

All participants who received as first active COVID-19 vaccination Ad26.COV2.S until the participant receives an outside COVID-19 vaccination. This includes participants who initially received placebo and subsequently received Ad26.COV2.S, however only the safety data after the Ad26.COV2.S vaccination until the participant receives an outside

COVID-19 vaccination (if applicable) will be presented here. The safety data of participants who received 2 or more Ad26.COV2.S vaccinations will be presented by post-dose 1, post-dose 2, etc.

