**B. Layout 1b:**

**1. mRNA/non-mRNA vaccination + Ad26.COV2.S**

All participants who received as first active COVID-19 vaccination one or more outside mRNA vaccinations or one or more outside non-mRNA vaccinations and subsequently also received an Ad26.COV2.S booster vaccination. Only the safety data after the Ad26.COV2.S vaccination until the participant receives another outside COVID-19 vaccination (if applicable) will be presented here. The safety data of participants who received 2 or more Ad26.COV2.S vaccinations after being primed with non-mRNA/mRNA will be presented by post-dose 1, post-dose 2, etc.

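### The rule that restarts Ad26.COV2.S post-dose numbering at 1 does not cover placebo, then outside vaccine, then Ad26.COV2.S, although layout 1b includes this sequence and counts doses from the first Ad26.COV2.S dose after priming

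*SAP*

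**What the plan says.** Three sets of statements in the SAP bear on this point.

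**Numbering (section 5.4.3).** Outside COVID-19 vaccines "will be included in the phase definitions as active vaccinations together with the study vaccinations". For reporting, the number of a post-dose period after Ad26.COV2.S is "restarted at 1 in case that previous vaccinations were only outside vaccinations (only mRNA or only non-mRNA vaccinations) or were only placebo injections".

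**Placebo (section 5.4.3).** Before Table 6: "Note, placebo vaccination between active vaccinations will be ignored". After Table 6, for participants who receive "placebo after an active vaccination, the placebo injection will not be counted as a study vaccination". For placebo given first: "For subjects that initially receive placebo and subsequently receive active vaccinations, separate post-dose periods will be created for the placebo injections and the active vaccinations".

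**Display (section 5.4.4).** The layout 1a placebo group keeps a participant's data "until the participant receives an active COVID-19 vaccination (Ad26.COV2.S or outside vaccination"), so the SAP foresees placebo recipients whose first active vaccine is an outside one. Layout 1b takes in "All participants who received as first active COVID-19 vaccination one or more outside mRNA vaccinations or one or more outside non-mRNA vaccinations" who later received Ad26.COV2.S. It shows only data after Ad26.COV2.S. Participants with two or more such doses after priming are shown by post-dose 1, post-dose 2 and so on. The second worked sequence in that section adds that the earlier outside vaccines must all be mRNA or all non-mRNA. Layouts 1a and 1b are tabulated by phase and period.

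**The concern.** Membership of layout 1b depends on the first active vaccination, so an earlier placebo injection does not exclude anyone. The restart rule looks at all previous vaccinations, and it has a branch for outside only and a branch for placebo only. It has none for placebo followed by outside vaccine.

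For participants enrolled in the double-blind phase this sequence follows from the design. The full analysis set requires a documented study vaccine, and on Day 1 that was Ad26.COV2.S or placebo. Anyone in that phase who took an outside vaccine after Day 1 and before a first Ad26.COV2.S dose must therefore have had placebo first.

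At stake is the dose-by-dose safety description of Ad26.COV2.S given on top of other vaccines. Section 5.4.6.2 uses the participants, or the person-years, in the given phase and vaccination group as denominator. A wrong period number therefore moves both events and person-time to another column.

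**Working it through.** No sample size or test is involved. The check applies the numbering rules of section 5.4.3 literally to vaccination sequences. P is placebo, M an outside mRNA dose, N an outside non-mRNA dose and A is Ad26.COV2.S.

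**Rules applied**
1. Each vaccination adds 1 to the post-dose number.
2. Placebo after an active vaccination is not counted.
3. At A, the number restarts at 1 if all previous vaccinations were M, or all were N, or all were P.

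For initial placebo followed by outside doses, rule 3 never applies at the first A, so:

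number of the first A = initial placebo injections + outside doses + 1.

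**Results for Ad26.COV2.S doses**

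| Sequence | Literal rule | Restart judged on previous active vaccinations only |
|---|---|---|
| P-A, P-P-A | 1 | 1 |
| M-A, M-M-A, N-A, M-P-A | 1 | 1 |
| P-M-A, P-N-A | 1 + 1 + 1 = 3 | 1 |
| P-P-M-A | 2 + 1 + 1 = 4 | 1 |
| P-M-M-A | 1 + 2 + 1 = 4 | 1 |
| P-P-M-M-A | 2 + 2 + 1 = 5 | 1 |
| P-M-A-A | 3, then 4 | 1, then 2 |
| P-M-N-A (mixed platforms) | 4 | 4 |

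**Can another sentence settle it?** The note before Table 6 covers placebo between active vaccinations. The sentence after the table covers placebo following an active vaccination. An initial placebo is neither, and it receives its own post-dose period. The placebo-only branch of the restart rule also implies that initial placebo counts, because otherwise that branch would be unnecessary.

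**Do first and second Ad26.COV2.S doses share a column?** Only in some sequences. The first dose of P-P-M-A and the second dose of P-M-A-A are both post-dose 4. Where numbering restarts properly, the second dose of M-A-A is post-dose 2. The misnumbered first doses start at 3, so none of them falls in that column.

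**Does the amended rule disturb anything?** The sequences already covered keep their numbers. P-M-N-A still does not restart, which agrees with the single-platform condition for layout 1b.

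**The case against.** The strongest reply is that section 5.4.4 already fixes the output. Layout 1b shows only data after Ad26.COV2.S and counts doses after priming, so a programmer following the table definition would label the first such dose post-dose 1. Section 5.4.3 also says that phases serve to build the datasets and are combined or renumbered for reporting. The intent is indeed clear, and a label of post-dose 3 or higher for someone with one Ad26.COV2.S dose might be noticed on review. But the restart sentence is itself the renumbering for reporting, and taken literally it gives a result that conflicts with section 5.4.4.

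A second reply is that the words "separate post-dose periods will be created for the placebo injections and the active vaccinations" could mean that placebo and active doses are numbered apart. The participant would then have only outside vaccinations before Ad26.COV2.S and would restart at 1. That reading is possible, but the sentence does not say so, and the placebo-only branch speaks against it.

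Three stronger readings are tempting and not supported:
- A reader might infer that counting active doses only would give post-dose 2 for P-M-A, and hence routine pooling with true second doses. If placebo is outside the count, the restart rule applies and the number is 1. The fault arises only when placebo counts, and the lowest wrong number is then 3.
- A reader might infer that most of layout 1b is affected. The SAP gives no count. Newly enrolled open-label participants receive no placebo, and the cross-over conditions are in protocol section 6.4, which is not at hand. Participants whose outside vaccine came before any study injection are numbered correctly.
- A reader might infer that the layout 1b rates will be wrong. That holds only if the rule is programmed as written.

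**Conclusion.** The point holds as a conflict between the restart rule in section 5.4.3 and the layout 1b display in section 5.4.4. As written, the rule numbers the first Ad26.COV2.S dose of placebo-first, outside-primed participants as post-dose 3, 4 or 5 in the sequences worked above. The same exposure without placebo is post-dose 1. The layout 1b post-dose 1 column would lose these participants' events and person-time, and first and second doses would mix in a few later columns.

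This rests on initial placebo counting in the sequence, which is the more natural reading of section 5.4.3, and on the rule being programmed literally. The number of participants is unknown. All safety tables are descriptive, no hypothesis test is touched, and the placebo data, layout 1a and the mixed-schedule layout are not affected. It should be corrected, because the rule gives a wrong result for a sequence that the plan itself assigns to this table.

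**What to change.** Amend the restart sentence in section 5.4.3 along these lines: for the numbering of Ad26.COV2.S post-dose periods only, numbering restarts at 1 when all previous active vaccinations were outside vaccinations of one platform (only mRNA or only non-mRNA), or when there were no previous active vaccinations, whether or not placebo was given earlier.

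Keep the limitation to this numbering. A general statement that placebo is disregarded would clash with the separate placebo post-dose periods in section 5.4.3, which the layout 1a placebo group needs.

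The cost is one sentence in the SAP and one condition in the derivation of the analysis datasets. No new data are needed.
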